7.9 Efficacy Analysis

Response will be assessed according to mRECIST 1.1 for all patients. Response will also be assessed according to iRECIST for patients in Phase 2 expansion cohort.

Best Overall Response (BOR)

Best overall response is defined as the best response (per investigator assessment as defined by mRECIST 1.1 or iRECIST Criteria) recorded after the first dose of the study drug until a subsequent anti-cancer therapy. Response assessments after treatment discontinuation but before the initiation of a subsequent anti-cancer therapy should be included in the analysis of BOR. This will be ordered from best to worst: Complete Response (CR or iCR), Partial Response (PR or iPR), Stable Disease (SD or iSD), Progressive Disease (PD, iUPD or iCPD), Not Evaluable (NE or iNE).

Waterfall plots for best percentage change in the size of target lesions as per mRECIST 1.1 criteria will also be presented. The plot will have the following information:

1. Response,
2. Dose,
3. Cohort
4. Phase (escalation, safety lead-in or expansion).

Best overall response will be summarized and listed for all patients in the response evaluable analysis set. Overall response will be listed for all patients in the response evaluable set for each visit along with percentage change in the size of target lesions per mRECIST 1.1 criteria. If target lesion is believed to be present but too small to measure, a value of 5 mm is assigned per mRECIST 1.1.

Overall Response Rate (ORR)

The ORR is defined as the proportion of patients who have achieved the best response of CR or PR during the study per investigator assessment as defined by mRECIST 1.1 or iRECIST Criteria. The ORR will be summarized by frequencies and percentages for patients in the response evaluable analysis set. A binomial exact confidence interval will also be provided when possible.

Disease Control Rate (DCR)

The DCR is defined as the proportion of patients who have achieved the best response of CR, PR or SD during the study per investigator assessment as defined by mRECIST 1.1 or iRECIST Criteria. The DCR will be summarized by frequencies and percentages for patients in the response evaluable analysis set. A binomial exact confidence interval will also be provided when possible.

Duration of Response (DOR)

The DOR will be tabulated for those patients with a CR or PR during the study per investigator assessment as defined by mRECIST 1.1 or iRECIST Criteria in the response evaluable analysis set with a reasonable number of responses. The DOR is defined as the number of days from the first documentation of a response until progressive disease or death, whichever occurs first. If a patient misses two consecutive disease assessments, then follow-up for the primary endpoint will be censored at the time of last non-progressive scan prior to the missed interval.

The censoring rules and censoring date in the analysis of DOR will be the same as for PFS and TTP.

$$\text{DOR (months)} = (\text{date of progression or death or censor} - \text{date of confirmed response} + 1) / 30.4375.$$

The Kaplan-Meier method will be used to estimate the distribution of DOR. The 25th, 50th (median), and 75th percentiles, and the corresponding 2-sided 95% confidence intervals (CIs) based on Brookmeyer and Crowley method (Brookmeyer and Crowley 1982), will be presented. The number of patients with events and the number of patients censored will be summarized. DOR for all patients with a response will be listed.

Progression Free Survival (PFS)

PFS is defined as the time from the date of first dose to the date of PD (or iCPD) (per investigator assessment as defined by mRECIST 1.1 or iRECIST Criteria) or the date of death due to any cause, whichever occurs first. Patients without documentation of PD (or iCPD) or death will be censored at the date of the last response assessment that is SD (iSD) or better, and prior to or on the date of initiation of alternative anti-cancer therapy if patients start new treatments. Patients with no post baseline response assessment will be censored on day 1.

$$\text{PFS (months)} = (\text{earliest date of progression or death or censor} - \text{date of first dose} + 1) / 30.4375.$$

The analysis of PFS will be based on the safety analysis set with a reasonable number of patients. The Kaplan-Meier method will be used to estimate the distribution of PFS. Kaplan-Meier survival curves, the 25th, 50th (median), and 75th percentiles, along with associated 2-sided 95% confidence intervals (CIs) based on Brookmeyer and Crowley method, and Kaplan-Meier PFS

probability estimates with 95% CIs at 3 and 6 months (or later time points if data permits) will be presented. The number of patients with events along with the type of events (death or progressive disease) and the number of patients censored will be summarized.

PFS for all patients in the safety analysis set will be listed.

Overall Survival (OS)

Overall survival in months is defined as the time from the date of first dose to the date of death of any cause [OS (months) = (date of death or censor – date of first dose + 1)/30.4375]. Patients without documentation of death at the time of analysis will be censored at the date last known to be alive.

The analysis of OS will be based on the safety analysis set with a reasonable number of patients. The Kaplan-Meier method will be used to analyze the distribution of OS. Kaplan-Meier survival curves, the 25th, 50th (median), and 75th percentiles, along with associated 2-sided 95% confidence intervals (CIs) based on Brookmeyer and Crowley method, and Kaplan-Meier estimates with 95% CIs at 6 and 12 months (or later time points if data permits) will be presented. The number of patients with events and the number of patients censored will be summarized.

OS for all patients in the safety analysis set will be listed.

Time to Progression (TTP)

Time to progression is defined as the time from first dose to the date of first documentation of objective progression. Patients without documentation of PD (iCPD) will be censored at the date of the last response assessment that is SD or better prior to the date of initiation of alternative anti-cancer therapy. Patients with no post baseline response assessment will be censored on day 1.

$TTP \text{ (months)} = (\text{date of progression or censor} - \text{date of first dose} + 1) / 30.4375$.

The Kaplan-Meier method will be used to estimate the distribution of TTP with a reasonable number of patients in the response evaluable set. Kaplan-Meier curves, the 25th, 50th (median), and 75th percentiles, along with associated 2-sided 95% confidence intervals (CIs) based on Brookmeyer and Crowley, and Kaplan-Meier estimates with 95% CIs at 3 and 6 months (or later time points if data permits) will be presented. The number of patients with events and the number of patients censored will be summarized.

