2. Although a rare event, response to immunotherapy may occur after appearance of PD, as assessed per conventional RECIST v1.1. In particular, small, new lesions may appear in the presence of other responsive target lesions (pseudoprogression).
3. Durable SD may represent antitumor activity of immunotherapy.

Therefore, RECIST v1.1 (Eisenhauer et al. 2009) will be implemented in this study as described below.

Contemporary immunotherapy protocols generally allow patients to continue treatment beyond initial radiographic evidence of progressive disease following further investigation, as accumulating data indicate it is possible that some patients treated with immunotherapy may derive clinical benefit beyond initial RECIST-defined progressive disease, which may not be captured by radiographic assessments. Therefore, despite an initial RECIST-defined PD, patients who are clinically stable and deriving benefit may remain on study until PD has been confirmed in subsequent imaging assessments. In this study, patients treated with modakafusp alfa will be permitted to continue treatment beyond initial RECIST v1.1-defined progressive disease if the following criteria are met:

1. Investigator-assessed overall clinical benefit from continued treatment with modakafusp alfa. The assessment of clinical benefit should consider whether the subject is clinically deteriorating and unlikely to receive further benefit from continued treatment.

2. Tolerance of study drug(s).
3. Stable performance status.
4. Treatment beyond progression will not delay an imminent intervention to prevent serious complications of progressive disease (eg, central nervous system [CNS] metastases).
5. Patient agrees to receive additional modakafusp alfa by signing a separate ICF informing of pseudoprogression and the potential risks and benefits of continuing treatment in these circumstances.

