The decision to continue treatment beyond initial RECIST v1.1-defined progression should be discussed with the medical monitor and documented in the study records. Such patients may remain on the study and continue to receive monitoring according to the protocol-defined SOEs. Any additional post-RECIST v1.1 progression imaging time points acquired in patients that are considered clinically stable should also be collected and when available, submitted to the imaging core laboratory vendor for storage and potential, retrospective central reading. In general, treatment should be discontinued permanently either upon unequivocal evidence of further progressive disease based on subsequent imaging assessment or upon investigator's assessment that the subject is unlikely to receive further clinical benefit with continued treatment. For rare situations when the confirmatory scan confirms progressive disease, but the investigator believes that continued treatment is appropriate, a decision will be made jointly by the investigator and sponsor. If the patient experiences rapid clinical deterioration as perceived by the investigator before the next scheduled radiographic assessment of original PD, the investigator can discontinue study treatment without further objective evidence of disease progression and report it as progression.

9.3.14.2 *Requested Prescreening Imaging and Exploratory Tumor Kinetic Modeling*

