13.4 Efficacy Analysis

Efficacy endpoints include ORR, DCR, DOR, PFS, and OS. No formal statistical tests will be performed for these efficacy endpoints.

ORR is defined as the proportion of patients who achieve CR or PR (determined by the investigator) during the study in response-evaluable population.

DCR is defined as the proportion of patients who achieve CR, PR, or SD (determined by the investigator) during the study in response-evaluable population.

DOR is the time from the date of first documentation of a PR or better to the date of first documentation of PD for responders (PR or better). Responders without documentation of PD will be censored at the date of last response assessment that is SD or better.

TTP is the time from the date of the first dose of study drug to the date of the first documentation of PD according to RECIST v1.1.

PFS is defined as the time from the date of the first dose of study drug to the date of first documentation of PD according to RECIST v1.1 or death due to any cause, whichever occurs first. Patients without documentation of PD or death will be censored at the date of the last response assessment that is SD or better.

OS is defined as the time from the date of first dose of study drug to the date of death due to any cause. Patients without documentation of death at the time of analysis will be censored at the date last known to be alive.

ORR and DCR will be summarized using descriptive statistics with 95% CIs. PFS and OS will be analyzed descriptively using the Kaplan-Meier method for the safety analysis set. DOR will also be analyzed using the Kaplan-Meier method for the response-evaluable analysis set.

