5.0 ANALYSIS ENDPOINTS

5.1 Primary Endpoints

The primary endpoints are:

- Frequency and severity of treatment-emergent adverse events (TEAE) according to the National Cancer Institute Common Terminology Criteria for Adverse Events (NCI CTCAE), Version 5.0 (phase 1b and phase 2 safety lead-in).
- Number of patients with DLTs (phase 1b and phase 2 safety lead-in).
- Number/percentage of patients with 1 or more SAEs (phase 1b and phase 2 safety lead-in).
- Number/percentage of patients with 1 or more TEAE leading to dose modification and/or treatment discontinuation (phase 1b and phase 2 safety lead-in).
- Overall response rate (ORR) (complete response [CR] + partial response [PR]) assessed according to modified Response Evaluation Criteria in Solid Tumors, Version 1.1 (mRECIST v1.1) for melanoma patients (phase 2 expansion).

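### The primary RECIST response rate has no cut-off at first progression, and duration of response has two different start dates and two different end points

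*SAP*

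**What the plan says.** **Best response.** SAP 7.9 defines one best-response window for both sets of criteria, running from first dose and closing only at new anti-cancer treatment: "recorded after the first dose of the study drug until a subsequent anti-cancer therapy". It adds: "Response assessments after treatment discontinuation but before the initiation of a subsequent anti-cancer therapy should be included in the analysis of BOR". Complete response, partial response (PR) and stable disease all rank above progressive disease (PD). Protocol 13.4 sets no limit at progression either: "ORR is defined as the proportion of patients who achieve CR or PR (determined by the investigator) during the study in response-evaluable population".

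**Scans after progression.** Protocol 9.3.14.1 expects them. It notes: "Although a rare event, response to immunotherapy may occur after appearance of PD, as assessed per conventional RECIST v1.1". It says that "patients who are clinically stable and deriving benefit may remain on study until PD has been confirmed in subsequent imaging assessments", and that "Any additional post-RECIST v1.1 progression imaging time points acquired in patients that are considered clinically stable should also be collected".

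**PFS.** Protocol 13.4 ends PFS at the "date of first documentation of PD according to RECIST v1.1 or death due to any cause, whichever occurs first". The SAP's PFS formula likewise takes the earliest progression date.

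**DOR.** The SAP's sentence defining DOR starts the clock at the first documented response and stops it at progression or death. The formula below it subtracts the date of a confirmed response instead. Neither document says whether a response must be confirmed. Protocol 13.4 and Table 6.a stop DOR at progression only, and 13.4 censors responders without progression at their last scan showing stable disease or better. The SAP also says that DOR takes its censoring from both PFS and TTP.

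**The concern.** The primary efficacy endpoint is ORR by RECIST v1.1, and iRECIST ORR is a separate secondary endpoint. A window that ignores RECIST progression lets the primary endpoint take in post-progression responses that the iRECIST analysis is there to capture. It can only raise the primary ORR. Disease control rate uses the same window, so stable disease recorded after progression would count there too. One patient could be a responder for ORR and, earlier, a progressor for PFS and TTP.

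The two DOR inconsistencies leave the start date to whoever programs the formula, and leave the status of a responder's death to whichever document is followed. The study is open-label, response is judged by the investigator, no endpoint committee is used, and central reading is only a possibility. A rule chosen after the data are seen would be post hoc.

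**Working it through.** The plan gives no figure to reproduce here: the target response rates and futility boundaries are redacted, and no formal test of ORR is planned. The check is a comparison of the texts, with examples to show size.

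**Inputs.** From the documents: up to 25 patients per cohort (protocol 13.1.2); scans every 6 weeks through Cycle 6, then every 9 weeks (protocol 9.3.14), hence at about weeks 6, 12, 18, 27 and 36; DOR in months = (end date − start date + 1)/30.4375 (SAP 7.9). Assumed for illustration: 5 responders as a base, and the week numbers of the example patients.

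**1. Best-response window.** Take a patient with RECIST PD at week 6 (day 42), treatment continued, PR at week 18 (day 126), and no new anti-cancer treatment.
- ORR under the SAP window: responder.
- PFS: event at day 42.
- DOR to first PD, the protocol's end point: (42 − 126 + 1)/30.4375 = −2.7 months.
- DOR to a later PD at week 36 (day 252), if the SAP is read as meaning progression after the response: (252 − 126 + 1)/30.4375 = 4.2 months.

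Each such patient adds 1/25 = 4 percentage points. With exact (Clopper-Pearson) 95% intervals, 5/25 = 20.0% (6.8 to 40.7%) becomes 6/25 = 24.0% (9.4 to 45.1%).

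**2. DOR start.** If the formula means the date of the confirming scan, and that is the next scheduled scan, DOR shortens by 42/30.4375 = 1.4 months or 63/30.4375 = 2.1 months.
- PR week 6, confirmed week 12, PD week 36: (252 − 42 + 1)/30.4375 = 6.9 months from first response; (252 − 84 + 1)/30.4375 = 5.6 months from confirmation.
- PR week 18, confirmed week 27, PD week 36: 4.2 months from first response; (252 − 189 + 1)/30.4375 = 2.1 months from confirmation.

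If it means the first date of a response that is later confirmed, confirmed responders lose nothing. Unconfirmed responders, who still count in ORR, then have no start date.

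**3. DOR end.** PR at week 6 (day 42), last scan without progression at week 27 (day 189), death at week 31 (day 217).
- SAP: event at (217 − 42 + 1)/30.4375 = 5.8 months.
- Protocol: censored at (189 − 42 + 1)/30.4375 = 4.9 months.

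The SAP's reference to PFS and TTP censoring does not help, because a death without progression is an event for PFS and not for TTP.

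**The case against.** The strongest objection is that SAP 7.9 does not define best response by its window alone. It also says response is as defined by the cited criteria, and those may bring in a stop at progression. The guideline is not part of the documents, so this cannot be settled here. It stands as a reason for caution: under that reading the first part is a clarification. But the SAP writes out its own window, ends it only at new treatment, and applies it unchanged to two sets of criteria that handle progression differently.

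A second objection is that the sponsor may want to count late responses, since protocol 9.3.14.1 asks for allowance for immunotherapy response patterns. The operative text of that section, however, governs whether treatment continues, and iRECIST ORR already provides a place for those responses.

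Third, the effect is small. This stands for ORR: the protocol calls post-progression responses rare, one such patient leaves the estimate well inside the base interval, and by-visit listings would show who is affected. The −2.7 months also depends on the protocol's end point; the SAP's wording can be read to give 4.2. Finally, DOR is a descriptive secondary endpoint, and the SAP's reference to PFS and TTP concerns censoring, not events. Both are true, but they do not remove the conflict between the SAP's definition and its formula, or between the SAP and the protocol over death.

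**Conclusion.** The concern holds in all three parts and should be fixed, though it is unlikely to change the trial's conclusions by itself. Followed as written, the SAP window makes ORR and PFS disagree for any patient who responds after RECIST progression, and gives that patient a negative DOR under the protocol's end point. The effect on ORR is 4 points per such patient in a cohort of 25, and zero if there are none; no rate is given. The DOR conflicts do not depend on that rate: 1.4 or 2.1 months per responder if the formula means the next scheduled scan, and event versus censored for any responder who dies without progression. Confidence in the first part is medium, because the unseen criteria could be read to override the stated window.

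The SAP's label mRECIST v1.1, where the current protocol says RECIST v1.1, is a version lag. The SAP's only response-criteria reference is the RECIST 1.1 guideline, so the label points to no separate rule on progression.

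**What to change.** 1. In SAP 7.9, for RECIST v1.1, close best response at the earlier of first PD or new anti-cancer treatment, and count later responses only under iRECIST. Change the mRECIST label to RECIST v1.1 throughout the SAP.
2. Start the DOR formula at the first documented response. State one confirmation rule, of the sponsor's choosing, and apply it to both ORR and DOR.
3. Use progression or death as the end of DOR in SAP 7.9, protocol 13.4 and Table 6.a, and let DOR take its censoring from PFS alone.

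The sponsor should also check that the response count in the futility analyses uses the same rule as the primary ORR.

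The cost is wording, with no new scans or data. The SAP edits can be made before database lock; the protocol edits need an amendment. The downside is that ORR may come out slightly lower.

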9.3.14 Disease Assessment

At screening, CT and/or MRI scans will be performed unless chest, abdominal cavity, and pelvis diagnostic quality scans were performed within 5 weeks before the planned first dose of study drug. CT and/or MRI scans of the chest, abdominal cavity, and pelvis should be acquired with at least IV contrast. The imaging modalities used for a patient should remain consistent throughout the study. If IV contrast-enhanced CT scans are contraindicated for a particular patient, a noncontrast-enhanced CT of the chest should be acquired in addition to an oral contrast-enhanced CT of the abdomen and IV contrast-enhanced pelvic MRI.

At present, low-dose or attenuation correction CT portions of a combined PET-CT are of limited use in anatomically based efficacy assessments, and it is therefore suggested that they should not be substituted for dedicated diagnostic contrast-enhanced CT scans for anatomically based

RECIST measurements. However, if a site can document that the CT performed as part of a PET–CT is of identical diagnostic quality to a diagnostic CT (with IV and oral contrast), then the CT portion of the PET–CT can be used for RECIST measurements. Note, however, that the PET portion of the CT introduces additional data that may bias an investigator if it is not routinely or serially performed.

Repeat CT and/or MRI scans should be performed every 6 weeks through Cycle 6 and every 9 weeks thereafter, and as clinically indicated.

Response assessment will be calendar-based regardless of treatment delays/interruptions. Investigator assessment of disease response and progression will be based on RECIST v1.1 (Section 9.3.14.1) and iRECIST (Seymour et al. 2017) (phase 2 expansion only). Screening and on-treatment images, when available, should be submitted to the imaging core laboratory vendor for storage and potential retrospective central reading.

In extenuating circumstances, such as during the COVID-19 public health emergency, patients may use an alternative site for imaging with prior notification to the sponsor or designee.

9.3.14.1 *RECIST v1.1 and Treatment Beyond Progression*

Because treatment decisions will be made based on local assessment by the investigator, when assessing response, special consideration should be given to the tumor response characteristics associated with immunotherapy:

1. Measurable tumor size reduction may require a longer treatment duration with immunotherapy than with a cytotoxic regimen.

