1.2 Summary of Changes

Summary of Changes from Version 2 to Version 3 of the SAP		
Location	Description	Rationale
Title Throughout SAP	Update the drug name from TAK-573 to modakafusp alfa.	Update according to PA4
Section 4.2.2 Secondary Objectives Section 4.2.3 Exploratory Objectives Section 5.2 Secondary Endpoints Section 5.3 Exploratory Endpoints	Downgraded the CD38 receptor occupancy objective and endpoint from secondary to exploratory.	Update according to PA4
Section 4.2.2 Secondary Objectives Section 4.2.3 Exploratory Objectives Section 5.2 Secondary Endpoints Section 5.3 Exploratory Endpoints	Downgraded the Type I interferon gene expression signatures objective and endpoint to exploratory.	Update according to PA4
Section 6.0 Determination of Sample Size Section 7.13 [REDACTED]	[REDACTED]	Update according to PA4
Section 6.0 Determination of Sample Size	Corrected “regresson” to “regression”.	Correction
Section 7.9 Efficacy Analysis	Added the size value of target lesion when it is too small to measure.	Clarification
Section 7.9 Efficacy Analysis	Added censoring rule for the primary analysis of DoR, PFS and TTP for patients who missed two consecutive disease assessments.	Clarification
Section 7.10.1.2 Serum PK Parameters	Added boxplot as well as regression analysis for PK parameters	Update
Section 7.12.1 Adverse Events	Updated the definition of “on-study deaths”	Update according to PA4
Section 7.12.1 Adverse Events	Added AESIs for both modakafusp alfa and pembrolizumab.	Update according to PA4
Appendix A By-Subject Listing	Added “status of non-target lesion, status of new lesion” for Efficacy.	Update
Appendix B Date Imputation Rules	Delete the imputation rules regarding “ongoing” flag for AE since this variable is not captured in the database.	Update

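### The two-missed-assessments rule in SAP 7.9 censors DOR, PFS and TTP on the gap alone, and conflicts with the general censoring rule with no stated precedence

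*SAP*

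**What the plan says.** The rule sits in the DOR paragraph of SAP 7.9: "If a patient misses two consecutive disease assessments, then follow-up for the primary endpoint will be censored at the time of last non-progressive scan". The same sentence sets the date: follow-up "will be censored at the time of last non-progressive scan prior to the missed interval". The next sentence carries it to the other endpoints: "The censoring rules and censoring date in the analysis of DOR will be the same as for PFS and TTP". SAP 1.2 confirms the scope in its list of changes: "Added censoring rule for the primary analysis of DoR, PFS and TTP for patients who missed two consecutive disease assessments".

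A second rule covers patients without an event. For PFS, SAP 7.9 says that they "will be censored at the date of the last response assessment that is SD (iSD) or better", and the TTP paragraph says much the same. Protocol 13.4 has the equivalent for DOR, "Responders without documentation of PD will be censored at the date of last response assessment that is SD or better", and for PFS. The Protocol has no missed-scan rule. Neither document says which rule prevails when both could apply.

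**The concern.** A missed-scan rule normally deals with one situation: progression or death is first found after a long unobserved interval, so its date is poorly known. The SAP sentence is not limited to that situation. It makes no exception for a patient who misses two scans, returns, and is scanned without progression.

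Read as the specific rule, it moves that patient's censoring date back to before the gap. The clean scans after return no longer count, and a later, properly dated progression or death is not counted as an event. The general rule would keep the follow-up of a returning patient who never progresses. Two programmers could therefore derive different DOR, PFS and TTP from the same data. Patients followed longest have the most scheduled scans, and so the most chances of a gap.

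The sentence also refers to 'the primary endpoint', but the phase 2 primary efficacy endpoint is ORR, which has no follow-up time to censor.

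**Working it through.** The documents give no event count or power that depends on this rule, so there is no planned figure to reproduce. The check has three parts.

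**1. The rules side by side**, for a patient who misses two consecutive scans:

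| What follows the gap | Gap rule | Rest of SAP 7.9 |
|---|---|---|
| No further scan, no event known | Censored at last clean scan before the gap | Same date |
| PD on the first scan after the gap | Censored before the gap | Event at that scan |
| Clean scans, never an event | Censored before the gap | Censored at last clean scan after the gap |
| Clean scans, then PD or death | Censored before the gap, event dropped | Event |

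Row 2 is the case such a rule is meant for. Rows 3 and 4 are the problem.

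**2. One assumed patient.** Protocol 9.3.14 sets the schedule: "Repeat CT and/or MRI scans should be performed every 6 weeks through Cycle 6 and every 9 weeks thereafter, and as clinically indicated". That gives scans at weeks 6, 12, 18, 27, 36, 45, 54, 63 and 72. Assume a response first documented at week 6, a clean scan at week 12, scans at weeks 18 and 27 missed, and clean scans from week 36 to week 72. SAP 7.9 computes months as (days + 1)/30.4375.

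- PFS, rule as written (week 12): (84 + 1)/30.4375 = 2.79 months.
- PFS, conditional rule (week 72): (504 + 1)/30.4375 = 16.59 months.
- DOR, rule as written (weeks 6 to 12): (42 + 1)/30.4375 = 1.41 months.
- DOR, conditional rule (weeks 6 to 72): (462 + 1)/30.4375 = 15.21 months.

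The difference is 420/30.4375 = 13.80 months for both endpoints. SAP 7.9 plans PFS estimates at 3 and 6 months. This patient is censored at 2.79 months, before both, despite a clean scan at week 36, which is (252 + 1)/30.4375 = 8.31 months.

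**3. Average effect in one cohort of 25** (SAP 6.0). Scans were simulated on the protocol schedule to week 99, comparing the rule as written with a conditional rule that censors before the gap only if the first scan after it shows PD. Assumptions not in the documents: exponential PFS, each scan missed independently, no deaths without PD. There were 1,500 simulated cohorts per setting.

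| Median PFS (months) | Scans missed | Patients returning clean, per 25 | PFS follow-up lost | PFS events, conditional → as written |
|---|---|---|---|---|
| 3 | 5% | 0.05 | 0.4% | 24.8 → 24.7 |
| 3 | 10% | 0.20 | 1.6% | 24.3 → 24.1 |
| 3 | 20% | 0.80 | 6.4% | 22.8 → 22.1 |
| 6 | 5% | 0.16 | 0.9% | 23.1 → 23.0 |
| 6 | 10% | 0.57 | 3.2% | 22.6 → 22.2 |
| 6 | 20% | 2.02 | 11.6% | 21.0 → 19.6 |
| 12 | 5% | 0.27 | 1.1% | 18.2 → 18.1 |
| 12 | 10% | 1.12 | 4.7% | 17.8 → 17.3 |
| 12 | 20% | 3.65 | 15.7% | 16.4 → 14.9 |

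**The case against.** The strongest reply is that the SAP contains its own answer. A patient with no documented progression or death is censored at the last assessment of stable disease or better, so the worked patient is kept to week 72 and nothing is lost. That reply stands in part: a reader might infer that the SAP certainly discards this time, and the documents do not settle it. But it does not remove the problem. The gap rule is the more specific of the two and would naturally override, and no precedence is stated. For a patient who returns clean and later progresses, the no-event rule does not apply at all.

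Three other strong readings go too far.

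- A reader might infer that a clean scan after the gap proves no progression occurred in between. Protocol 9.3.14.1 allows that a response can, rarely, follow RECIST-defined progression. After an 18- to 27-week gap, intervening progression is unlikely but not excluded.
- A reader might take the COVID-19 provisions (Protocol 9.3 and 9.3.14) as an expectation of missed scans. They permit alternative visit methods and imaging sites, which are ways to avoid missing them.
- A gap placed directly after the first response would give a more dramatic DOR, but that is an extreme case. It also depends on where DOR starts, because SAP 7.9 defines it from first documentation while its formula uses the date of confirmed response. The 13.80-month difference in the worked patient does not depend on that choice.

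It is also fair to say that the reference to the primary endpoint is a slip whose meaning SAP 1.2 makes clear, and that the PFS and TTP paragraphs need not repeat a rule that reaches them by cross-reference. The response assessments and time-to-event data are listed by patient (SAP Appendix A), so excluded time could be recovered.

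**Conclusion.** The rule should be corrected. As worded, it applies to any two consecutive missed assessments, dates the censoring before the gap, and covers DOR, PFS and TTP. It also conflicts with the general censoring rule. The loss occurs if the gap rule is applied as the specific one.

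The effect on one patient can be large: 13.80 months in the illustration. The average effect is modest. At an assumed 6-month median PFS with 10% of scans missed, it is 3.2% of PFS follow-up and 0.4 of an event per cohort (22.6 − 22.2). The 15.7% upper end needs 20% of scans missed and a 12-month median. The documents give no miss rate, so these are ranges and not forecasts. If gaps are unrelated to outcome, the loss is mainly of precision; bias arises only if they are related.

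A reader might infer that the trial's main efficacy result is at risk. It is not: ORR is unaffected, and DOR, PFS and TTP are secondary endpoints with no formal tests (Protocol 13.4).

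**What to change.** State the rule once in SAP 7.9 for all three endpoints, for example:

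*If PD or death is first documented immediately after two or more consecutive missed disease assessments, the patient is censored at the last non-progressive assessment before the gap. If the next assessment after the gap shows no PD, the patient remains in follow-up and the general censoring rule applies.*

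Say that the pre-gap censoring takes precedence over the general rule in the first case only, and replace 'the primary endpoint' with 'DOR, PFS and TTP'. Do not add non-evaluable assessments as a trigger. The SAP does not use them as one now, and doing so would censor further true events.

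The cost is a short change of SAP wording and one derivation. Trial conduct and data collection do not change.
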